3.4 Secondary Efficacy Endpoints

The secondary efficacy endpoints are:

- PD measurement at week 24 compared to baseline in patients with baseline PD measurement of 6-8 mm inclusive.
- Bleeding on Probing (BOP) measurements at week 16 and 24 compared to baseline.
- PD measurement at week 16 compared to baseline.

The analysis of the secondary endpoints will be based on ITT, mITT, PP and PP2 populations.

Multiplicity

The secondary efficacy endpoints will be analysed according to pre-defined order:

1. PD changes at 24 weeks from baseline in patients with baseline PD of 6-8 mm inclusive.
2. BOP changes at 24 weeks from baseline
3. BOP changes at 16 weeks from baseline
4. PD changes at 16 weeks from baseline

The following stages will be applied:

1. The 1st secondary endpoint in the ordered list will be tested at 5% significance level. If it achieves statistical significance then the 2nd secondary endpoint will be analysed (stage 2). Otherwise the other secondary endpoints in the list will not formally be tested.
2. The 2nd secondary endpoint in the ordered list will be tested at 5% significance level. If it achieves statistical significance then the 3rd secondary endpoint will be analysed (stage 3). Otherwise the other secondary endpoints in the list will not formally be tested.
3. The process will continue for all the secondary endpoints according to the list until a secondary endpoint is not significant or until all secondary endpoints have been found significant.

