1. INTRODUCTION

1.1 Objectives

This document details the statistical analysis that will be performed for the Dexcel Pharma Technologies, Ltd. study CLI/016P. The statistical methods described in the SAP are elaboration of the statistical section included in the study protocol.

The primary objective of the study is to compare the mean probing Pocket Depth (PD) reductions (absolute change) for the selected target implant/s at week 24 compared to baseline.

The secondary objectives of the study are:

- PD measurement at week 24 compared to baseline in patients with baseline PD measurement of 6-8 mm inclusive.
- Bleeding on Probing (BOP) measurements at week 16 and 24 compared to baseline.
- PD measurement at week 16 compared to baseline

The exploratory objectives of the study are:

- PD, BOP and Relative Attachment Levels (RAL) measurements at week 24 compare to baseline in Responders patients. Responder patients are those patients which demonstrated at week 24 PD reduction of at least 1 mm from baseline PD of 5 mm or PD reduction of at least 2 mm from baseline PD of 6-8 mm inclusive.
- PD and BOP measurements at weeks 8 and 12 compared to baseline.
- Recession (R) and RAL measurements at weeks 8, 12, 16 and 24 compare to baseline.
- PD measurement at week 12 and 16 compared to week 24.
- PD, BOP, RAL and R measured at weeks 8, 12, 16 and 24 for all 4 sites (mesio-buccal, mid-buccal, disto-buccal and mid-lingual), surrounding the selected target implant/s, compared to baseline.

The safety objective of the study is to assess the safety of the PerioChip®.

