2. STATISTICAL METHODS

2.1 General

The change in efficacy parameters, PD, R and RAL during the 24 week treatment, will be modelled using a linear-mixed model (SAS® 9.3 Mixed Procedure) with treatment as fixed factors. Patient and pocket will be entered as random effects. The treatment-by-center interaction will be tested and if achieve statistical significance of $\leq 5\%$ will be added to the model as covariate. The analysis will be adjusted to the following covariates known to have influence on the efficacy parameters: age, gender, smoking status and baseline measurements. The adequacy of the Mixed Model will be checked and if needed a normalizing transformation will be performed. This model will be used for the reduction in PD, R and for improvement in RAL.

Contrasts with 95% Confidence Interval (C.I.) for the difference or ratio between the changes will be computed.

The Paired T-test or Signed rank test for two means (paired observations) (as is appropriate) will be applied for testing the statistical significance of the decrease in PD at each time point within each study group.

The two-sample T-test or Non-parametric Wilcoxon-Mann-Whitney Rank sum test for independent samples (as is appropriate) will be applied for testing the statistical significance of the difference in the percent PD decrease from baseline between the study groups.

Patients may have multiple pockets being treated. All treated pockets will be taken into account to create a by-pocket analysis in addition to the by-patient analysis.

Corresponding 95% C.I. for the difference between treatments not including zero for linear model, or 95% C.I. for the ratios between treatments not including unity for the log-linear regression will prove superior to treatment with PerioChip® versus Subgingival debridement.

Analysis for the number of pockets with at least 1 mm and at least 2 mm reduction in PD, and analysis for BOP for the target implant/s measured at each visit will be analyzed by a Chi-square test or Fisher's exact test as is appropriate.

Logistic regression will be applied for testing the above differences with adjustment to smoking status, Gingival Index (GI), medical center and other suspected confounders, if found. Odds Ratio and 95% Confidence Interval will be calculated using the Logistic model.

Similar mixed models for PD, R and RAL with time as a fixed repeated covariate will be used to reveal the changes of these parameters over time.

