3.3 Primary Efficacy Endpoint

At week 24, compared to baseline, the mean probing Pocket Depth (PD) reductions (absolute change) for the selected target implant/s will be used as the primary efficacy endpoint. The analysis of the primary endpoint will be based on ITT, mITT, PP and PP2 populations, by-pocket and by-patient analyses.

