3.3.1 Principal Analysis

The change in efficacy parameters, PD, during the 24 week treatment, will be modelled using a linear-mixed model (SAS® 9.3 Mixed Procedure) with treatment as fixed factors. Patient and pocket will be entered as random effects. Interactions between treatment and the covariates will be tested and if achieve statistical significance of $\leq 5\%$ will be added to the model as covariate. The analysis will be adjusted to the following covariates known to have influence on the efficacy parameters: age, gender, smoking status, site and baseline measurements. The adequacy of the Mixed Model will be checked and if needed a normalizing transformation will be performed.

Contrasts with 95% C.I. for the difference between the changes by week will be computed.

The Paired T-test or Signed rank test for two means (paired observations) (as is appropriate) will be applied for testing the statistical significance of the decrease in PD at each time point within each study group.

The two-sample T-test or Non-parametric Median test for independent samples (as is appropriate) will be applied for testing the statistical significance of the difference in the PD decrease from baseline between the study groups.

Categorical analysis will be applied for PD change at week 24, using median value calculated overall subjects. Logistic regression will be applied for categorical PD change with adjustment to baseline measure, age, gender, site and smoking status. Interactions between treatment and the covariates will be tested and if found statistically significant, will be added to the model.

Analysis of Variance (ANOVA) will be applied for analysing PD change at week 24, with adjustment to baseline measure, age, gender, site and smoking status. Interactions between treatment and the covariates will be tested and if found statistically significant, will be added to the model.

Missing data will be handled for imputation the primary endpoint data using the MMRM model (Mixed-effect Model for Repeated Measures), which is based on MAR (missing at random) assumption.

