3.5 Exploratory Analysis

- PD, BOP and RAL measurements at week 24 compare to baseline in Responders patients. Responders patients are those patients which demonstrated at week 24 PD reduction of at least 1 mm from baseline PD of 5 mm or PD reduction of at least 2 mm from baseline PD of 6-8 mm inclusive.
- PD and BOP measurements at weeks 8 and 12 compared to baseline.
- Recession (R) and Relative Attachment Levels (RAL) measurements at weeks 8, 12, 16 and 24 compare to baseline.
- PD measurement at week 12 and 16 compared to week 24.
- PD, BOP, RAL and R measured at weeks 8, 12, 16 and 24 for all 4 sites (mesio-buccal, mid-buccal, disto-buccal and mid-lingual), surrounding the selected target implant/s, compared to baseline.

The statistical methods described in the subsequent paragraphs will be used for analysis of both primary and secondary endpoints. The change in efficacy parameters, PD, R and RAL during the 24 week treatment, will be modelled using a linear-mixed model (SAS® 9.3 Mixed Procedure) with treatment as fixed factors. Patient and pocket will be entered as random effects. The interactions between treatment and the covariates will be tested and if achieve statistical

significance of $\leq 5\%$ will be added to the model as covariate. The analysis will be adjusted to the following covariates known to have influence on the efficacy parameters: age, gender, smoking status and baseline measurements. The adequacy of the Mixed Model will be checked and if needed a normalizing transformation will be performed. This model will be used for the reduction in PD, R and for improvement in RAL.

Contrasts with 95% C.I. for the difference between the changes by week will be computed.

The Paired T-test or Signed rank test for two means (paired observations) (as is appropriate) will be applied for testing the statistical significance of the decrease in PD at each time point within each study group.

The two-sample T-test or Non-parametric Median test for independent samples (as is appropriate) will be applied for testing the statistical significance of the difference in the PD decrease from baseline between the study groups.

Patients may have multiple pockets being treated. All treated pockets will be taken into account to create a by-pocket analysis in addition to the by-patient analysis.

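### The ordered secondary tests start at the full 5% with no stated condition that the primary test has succeeded, so a 6-8 mm subgroup claim after a failed primary is not excluded

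*SAP*

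**What the plan says.** The multiplicity text in SAP 3.4 is the only such rule in the available documents. It lists, in order, week-24 PD change in patients with baseline PD 6-8 mm, BOP at week 24, BOP at week 16, and PD at week 16. On entry it says: "The 1st secondary endpoint in the ordered list will be tested at 5% significance level". Each later endpoint is tested only if the preceding secondary is significant, and the stopping rule refers to secondary results alone. The primary is neither in the list nor a starting condition. SAP 1.8 and 2.1 set 5%, two-sided, for all comparisons, and SAP 1.9 plans no interim look.

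The primary is absolute PD change at week 24 in the target implants. SAP 3.3 adds: "The analysis of the primary endpoint will be based on ITT, mITT, PP and PP2 populations, by-pocket and by-patient analyses". SAP 3.3.1, titled Principal Analysis, gives a mixed model with patient and pocket as random effects, adjusted for "age, gender, smoking status, site and baseline measurements". It then adds a t-test or median test, a median-split logistic regression and an ANOVA. "Interactions between treatment and the covariates will be tested and if achieve statistical significance of" 5% or less, they enter the model. SAP 2.1 names only one interaction: "The treatment-by-center interaction will be tested and if achieve statistical significance of" 5% or less. SAP 3.5 adjusts for "age, gender, smoking status and baseline measurements", without site, yet says: "The statistical methods described in the subsequent paragraphs will be used for analysis of both primary and secondary endpoints".

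On its relation to the protocol, SAP 1.1 says: "The statistical methods described in the SAP are elaboration of the statistical section included in the study protocol".

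**The concern.** A fixed sequence controls error within its own list. Here that list starts after the primary and has its own 5%. The primary has another 5%. Without a link, the two families together have no 5% guarantee; adding the levels gives only a ceiling of 5% + 5% = 10%.

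The position of the gap matters. The first secondary is the same measure at the same visit in the deeper pockets, which makes it the natural fallback if the whole-population comparison fails. As written, that fallback could be reported as a formal success, and BOP and week-16 PD could follow it.

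A link to the primary needs one result to act on. SAP 3.3 and 3.3.1 list several populations, two units and several tests, so a bare reference to a significant primary would leave room for argument about which result opens the sequence.

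**Working it through.** **Step 1. The plan's own figure.** Inputs from SAP 1.8: 123 per arm, difference 0.50 mm, SD 1.30, two-group t-test, two-sided 5%.

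- Noncentrality = 0.50 / (1.30 × √(2/123)) = 3.016, with 244 degrees of freedom and critical value 1.970.
- Power = 85.2%, so the stated 85% is reproduced.
- At 15% drop-out, 246 / 0.85 = 289.4, which rounds up to the stated 290.

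**Step 2. Joint error without a link.** Let f be the share of analysed patients with baseline PD 6-8 mm. The documents do not give f, so a range is used. Also assumed are equal SD in both depth groups, equal allocation within them, and one patient-level test per endpoint. The whole-population difference is f × (subgroup difference) + (1 − f) × (difference in the rest). With n per arm:

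- variance, whole population = 2σ²/n
- variance, subgroup = 2σ²/(nf)
- covariance = f × 2σ²/(nf) = 2σ²/n
- correlation = (2σ²/n) / √[(2σ²/n) × (2σ²/(nf))] = √f

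With Z1 for the primary, Z2 for the subgroup and critical value 1.96:

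- any false positive, two-sided = 1 − P(|Z1| < 1.96 and |Z2| < 1.96)
- false claim for the chip = 1 − P(Z1 < 1.96 and Z2 < 1.96)

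| f | √f | Two-sided | Excess over 5% (points) | For the chip | Excess over 2.5% (points) |
|---|---|---|---|---|---|
| 0.9 | 0.949 | 6.48% | 1.48 | 3.24% | 0.74 |
| 0.8 | 0.894 | 7.09% | 2.09 | 3.54% | 1.04 |
| 0.5 | 0.707 | 8.31% | 3.31 | 4.16% | 1.66 |
| 0.3 | 0.548 | 8.93% | 3.93 | 4.47% | 1.97 |
| 0.2 | 0.447 | 9.21% | 4.21 | 4.61% | 2.11 |

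The excess is the probability that the subgroup is significant when the primary is not. If every null is true, the later secondaries add nothing, because they are reached only through the first. A simulation of 2,000,000 draws at f = 0.5 gave 8.3% without a link and 5.0% with one.

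**Step 3. How often the situation could arise when the chip works.** Take 0.50 mm, SD 1.30 and 123 per arm.

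- Effect only in the 6-8 mm group: the mean of Z1 is f × 0.50 / (1.30 × √(2/123)) and the mean of Z2 is 0.50 / (1.30 × √(2/(123f))). At f = 0.5 these are 1.508 and 2.133. A significant subgroup with a failed primary then occurs in about 28% of trials (27% at f = 0.3, 18% at f = 0.7).
- Same effect in all patients: 1.3% at f = 0.3, 1.6% at 0.5 and 1.8% at 0.7.

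These are not false positives. They show that the plan needs an answer for this outcome.

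**The case against.** The strongest reply is that the link may exist elsewhere or be implied. The public protocol file is a summary of changes, the SAP describes itself as elaborating a statistical section that is not in it, and two parts of the SAP were not available. A condition in any of these cannot be excluded. A reader might infer that the trial has no such condition at all; the documents do not support that. What stands is narrower: the rule in SAP 3.4, which spells out every other condition, does not state this one.

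A second reply is that only results in favour of the chip lead to a claim, so the relevant excess is 0.7 to 2.1 points and not the larger two-sided figure. That is fair, and the one-directional figure should lead. The figures also rest on an assumed subgroup share and on patient-level tests, whereas the secondary tables in Appendix I are all by-pocket.

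Three stronger readings are tempting and should be resisted.

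- A reader might treat four populations by two units as eight chances to win on the primary. The SAP gives more direction than that. SAP 1.4 uses mITT to confirm, SAP 2.1 and 3.5 describe the by-pocket analysis as additional to the by-patient one, and SAP 3.3.1 puts the mixed model first.
- A reader might call the site covariate wholly undecided. SAP 3.3.1 is the section specific to the primary, and it includes site. The statement in SAP 3.5 that its methods also serve the primary leaves an inconsistency to tidy, and no more.
- A reader might note that five interaction tests at 5%, if independent, admit at least one term in 1 − 0.95⁵ = 22.6% of trials with no true interaction, and call this error inflation. It is only the frequency with which a term enters the model. The documents give no basis for turning it into a false-positive rate for treatment.

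**Conclusion.** The point holds in this form. The stated rule opens the secondary sequence at the full 5% without reference to the primary, so following it permits a formal 6-8 mm claim after a failed primary. Under the null, the chance of a false claim for the chip from the primary or first secondary is 3.2% to 4.6%, against 2.5%, for subgroup shares of 90% down to 20%. The 5% level is exceeded at every share in that range. Within the secondary list the ordering is sound, and the sample size reproduces.

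The size depends on the assumed share, equal SDs and one patient-level test per endpoint. Whether the trial truly lacks the condition depends on text that is not available, so confidence in the gap is good for SAP 3.4 and only moderate for the plan as a whole.

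**What to change.** **1. Add to SAP 3.4:** *The secondary sequence is formally tested only if the primary analysis is significant at two-sided 5%; each step is decided in the ITT population.* If the protocol already holds this condition, a cross-reference in 3.4 makes it visible.

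**2. Name the deciding primary analysis in SAP 3.3 and 3.3.1,** so that the condition has one trigger: the week-24 treatment contrast in absolute mm, from the 3.3.1 mixed model in ITT, with the patient and pocket random effects already specified and the 3.3.1 covariates including site, without interactions selected by significance. Keeping site agrees with the randomization stratified by site (protocol summary of changes, Randomization Code); SAP 2.1 and 3.5 should be aligned. The following then become supportive: mITT, PP, PP2, the other unit of analysis, the t-test or median test, the median-split logistic regression, the ANOVA and the interaction models. If the sponsor prefers a by-patient mean as the deciding unit, the pocket random effect must come out of that model, because averaging leaves no pocket level.

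**Cost.** The condition uses no alpha. The primary plus ordered secondaries return to at most 5%, and 123 per arm still gives 85.2% power. The secondary tables need not be rebuilt by-patient. The price is that a subgroup or supportive result after a failed primary cannot be claimed as confirmatory. If the sponsor expects the benefit mainly in deep pockets, that price is real, as Step 3 shows. Both changes need to be dated before the treatment comparison is seen.

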3.5 Exploratory Analysis

- PD, BOP and RAL measurements at week 24 compare to baseline in Responders patients. Responders patients are those patients which demonstrated at week 24 PD reduction of at least 1 mm from baseline PD of 5 mm or PD reduction of at least 2 mm from baseline PD of 6-8 mm inclusive.
- PD and BOP measurements at weeks 8 and 12 compared to baseline.
- Recession (R) and Relative Attachment Levels (RAL) measurements at weeks 8, 12, 16 and 24 compare to baseline.
- PD measurement at week 12 and 16 compared to week 24.
- PD, BOP, RAL and R measured at weeks 8, 12, 16 and 24 for all 4 sites (mesio-buccal, mid-buccal, disto-buccal and mid-lingual), surrounding the selected target implant/s, compared to baseline.

The statistical methods described in the subsequent paragraphs will be used for analysis of both primary and secondary endpoints. The change in efficacy parameters, PD, R and RAL during the 24 week treatment, will be modelled using a linear-mixed model (SAS® 9.3 Mixed Procedure) with treatment as fixed factors. Patient and pocket will be entered as random effects. The interactions between treatment and the covariates will be tested and if achieve statistical

significance of $\leq 5\%$ will be added to the model as covariate. The analysis will be adjusted to the following covariates known to have influence on the efficacy parameters: age, gender, smoking status and baseline measurements. The adequacy of the Mixed Model will be checked and if needed a normalizing transformation will be performed. This model will be used for the reduction in PD, R and for improvement in RAL.

Contrasts with 95% C.I. for the difference between the changes by week will be computed.

The Paired T-test or Signed rank test for two means (paired observations) (as is appropriate) will be applied for testing the statistical significance of the decrease in PD at each time point within each study group.

The two-sample T-test or Non-parametric Median test for independent samples (as is appropriate) will be applied for testing the statistical significance of the difference in the PD decrease from baseline between the study groups.

Patients may have multiple pockets being treated. All treated pockets will be taken into account to create a by-pocket analysis in addition to the by-patient analysis.

Analysis for the number of pockets with at least 1 mm and at least 2 mm reduction in PD, and analysis for BOP for the target implant/s measured at each visit will be analyzed by a Chi-square test or Fisher's exact test as is appropriate.

Logistic regression will be applied for testing the above differences with adjustment to smoking status, GI, medical center and other suspected confounders, if found. Odds Ratio and 95% Confidence Interval will be calculated using the Logistic model.

Similar mixed models for PD, R and RAL with time as a fixed repeated covariate will be used to reveal the changes of these parameters over time.

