14.2-3.12	Summary Statistics of Pocket Depth (PD) Change at week 16 for target implants (by-pocket, PP2)
14.2-4	Exploratory Analyses
14.2-4.1	Changes of Pocket Depth (PD) at week 24 from baseline for responder patients (by-pocket, ITT)
14.2-4.2	Changes of Relative Attachment Levels (RAL) at week 24 from baseline for responder patients (by-pocket, ITT)
14.2-4.3	Changes of Bleeding on Probing (BOP) at week 24 from baseline for responder patients (by-pocket, ITT)
14.2-4.4	Summary statistics of Pocket Depth (PD) change at weeks 8 and 12 for target implants (by-pocket, ITT)
14.2-4.5	Summary statistics of Bleeding on Probing (BOP) change at weeks 8 and 12 for target implants (by-pocket, ITT)
14.2-4.6	Summary of Recession (R) Changes at weeks 8, 12, 16 and 24 for target implants (by-pocket, ITT)
14.2-4.7	Summary of Relative Attachment Levels (RAL) Changes at weeks 8, 12, 16 and 24 for target implants (by-pocket, ITT)
14.2-4.8	Summary of Pocket Depth (PD) Changes at weeks 8, 12, 16 and 24 for all aspects (by-pocket, ITT)
14.2-4.9	Summary of Bleeding on Probing (BOP) Changes at weeks 8, 12, 16 and 24 for all aspects (by-pocket, ITT)
14.2-4.10	Summary of Relative Attachment Levels (RAL) Changes at weeks 8, 12, 16 and 24 for all aspects (by-pocket, ITT)
14.2-4.11	Summary of Recession (R) Changes at weeks 8, 12, 16 and 24 for all aspects (by-pocket, ITT)

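### The exploratory responder analysis selects patients on their week-24 pocket-depth outcome; it should be descriptive only, with the proportion of responders by arm analysed instead

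*SAP*

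**What the plan says.** The first exploratory item in SAP 3.5 is "PD, BOP and RAL measurements at week 24 compare to baseline in Responders patients". It thus covers pocket depth (PD), bleeding on probing (BOP) and relative attachment level (RAL) in responders only. The same item appears as an exploratory objective in SAP 1.1 and among the exploratory endpoints in SAP 1.6.

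The definition depends on baseline depth and uses the week-24 result: "Responders patients are those patients which demonstrated at week 24 PD reduction of at least 1 mm from baseline PD of 5 mm". For pockets of 6 to 8 mm at baseline, the threshold is 2 mm instead. Week-24 PD reduction is also the primary endpoint (SAP 1.5).

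Three tables are planned. Table 14.2-4.1 is titled "Changes of Pocket Depth (PD) at week 24 from baseline for responder patients (by-pocket, ITT"; Tables 14.2-4.2 (RAL) and 14.2-4.3 (BOP) have the same form.

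Further down SAP 3.5, the change in PD, R and RAL "will be modelled using a linear-mixed model (SAS® 9.3 Mixed Procedure) with treatment as fixed factors", and paired tests of the PD decrease within each arm are added. The sentence introducing these methods reads "The statistical methods described in the subsequent paragraphs will be used for analysis of both primary and secondary endpoints". It does not mention the responder analysis.

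**The concern.** For PD, the variable that selects the patients is the variable then analysed. This has two consequences.

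- **Within an arm.** A patient enters the subset only by having a PD reduction at or above the cut-off. A paired test of decrease from baseline will therefore succeed whatever the treatment does.
- **Between arms.** If the chip works, the two arms contribute different fractions of their patients. Those whom the chip moves over the threshold enter the subset with reductions just above it and pull the treated mean down, while their counterparts in the control arm are left out. The contrast is no longer between randomised groups. BOP and RAL are exposed to the same selection to the extent that they correlate with PD reduction.

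The ITT label on the three tables adds to the risk of misreading, because SAP 1.4 defines ITT as all randomised and treated patients.

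**Working it through.** **Inputs.** SAP 1.8 gives mean PD reductions of 2.29 and 1.79 mm, SD 1.30, two-sided alpha 0.05, 85% power and 123 per arm. SAP 3.5 gives responder cut-offs of 1 mm (baseline 5 mm) and 2 mm (baseline 6-8 mm). Two things are assumed: reductions are normal with the same mean at every baseline depth, and the share of patients at 5 mm, which the documents do not give, is varied from none to all.

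**The plan's own figure.** n = 2 × (1.960 + 1.036)² × 1.30² / 0.50² = 121.4, so 122 by the normal approximation. The t-test calculation gives 122.4, rounded up to 123, with 85.2% power at 123. The SAP's figure is reproduced.

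**Means among responders.** For cut-off c and arm mean μ, put a = (c − μ)/1.30. The responder proportion is p = 1 − Φ(a), and the mean reduction among responders is μ + 1.30 × φ(a)/p. For example, with c = 2:

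- Chip: a = (2 − 2.29)/1.30 = −0.223, p = 0.588, mean 3.150 mm.
- Control: a = (2 − 1.79)/1.30 = 0.162, p = 0.436, mean 2.965 mm.
- Difference: 0.185 mm.

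The same calculation at both cut-offs, with and without rounding to whole millimetres:

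| Cut-off | Rounding | Responders, chip v control | Mean among responders, chip v control (mm) | Difference (mm) |
|---|---|---|---|---|
| 1 mm | none | 83.9% v 72.8% | 2.668 v 2.382 | 0.29 |
| 2 mm | none | 58.8% v 43.6% | 3.150 v 2.965 | 0.19 |
| 1 mm | whole mm | 91.6% v 83.9% | 2.520 v 2.186 | 0.33 |
| 2 mm | whole mm | 72.8% v 58.8% | 2.911 v 2.693 | 0.22 |

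The rows are the extremes in which all patients start at 5 mm or all at 6-8 mm. As one illustration in between, with 40% at 5 mm and whole-mm values, the responder proportions are about 80% and 69% and the difference is 0.29 mm. The true difference is 0.50 mm in every case.

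**Size and power of the subset (no rounding).** Of 123 per arm, about 72 v 54 (all 6-8 mm) to 103 v 90 (all 5 mm) are responders. Power for the responder-only contrast is about 26% to 52%. Power for comparing the responder proportion in everyone is about 56% to 67%.

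**Spill-over to another outcome.** Take an outcome such as RAL that the chip does not affect, with SD 1.30 and an assumed correlation of 0.3 to 0.7 with PD reduction. If the chip does improve PD by 0.50 mm, restricting to responders creates a false difference of about 0.06 to 0.22 mm against the chip.

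**The case against.** The case for leaving the plan alone has four parts.

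- **No between-arm comparison is stated.** The item and the table titles speak of change from baseline, and the models are assigned to primary and secondary endpoints. A reader might infer that the SAP commits to comparing arms within responders; the text does not say so. The inference is not far-fetched, since the SAP describes its primary endpoint in the same compared-to-baseline terms, and the model covers R and RAL, which are only exploratory. What stands is that the SAP leaves the question open.
- **Dichotomised PD analyses already exist.** SAP 2.1 and 3.5 plan counts of pockets with reductions of at least 1 mm and at least 2 mm, with chi-square or Fisher tests and an adjusted logistic model. SAP 3.3.1 adds a logistic model for PD change split at the overall median. A reader might infer that the responder contrast has been thrown away; that goes too far. Neither analysis uses the SAP's own patient-level, baseline-dependent definition, however, and Appendix I lists no table for either.
- **Nothing confirmatory rests on it.** The analysis is outside the ordered secondary testing in SAP 3.4. Week-24 PD, BOP and RAL are all analysed without the restriction. This stands in full.
- **The bias is against the chip.** If the chip works, the restriction understates its benefit; if it affects no outcome, selection is alike in both arms and no false difference arises. This also stands, so the risk is a misread table, not a spurious claim of efficacy.

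**Conclusion.** The point holds as a flaw in one exploratory analysis. Read within arms, the PD result is largely fixed by the definition of a responder. Read between arms, it is a non-randomised comparison in which a true 0.50 mm difference would appear as about 0.19 to 0.33 mm. That range rests on the SAP's means and SD, normal reductions, an equal mean reduction at every baseline depth, an unknown baseline mix and the choice of rounding; the shrinkage is present in every case computed.

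The documents do not support the stronger reading that the trial's efficacy conclusions are at risk: the primary and secondary analyses do not use the responder subset. The real gap is the missing proportion of responders by arm under the SAP's definition, which on the same inputs would be about 59% v 44% to 92% v 84%. The change is worth making because it is cheap and the analysis is a named objective with three tables.

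**What to change.** In SAP 1.1, 1.6 and 3.5, and in Appendix I:

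- Make the exploratory responder analysis the proportion of responders by arm in all ITT patients, using a logistic model with site, smoking and baseline PD, and give it a table.
- For missing week-24 PD, derive responder status from values imputed under the same missing-at-random assumption as the primary analysis. The mixed model in SAP 3.3.1 is for continuous PD and does not by itself classify a patient.
- State how a patient with two target implants is classified. The definition is per patient, but the tables are by pocket.
- Present PD, BOP and RAL changes within responders as description only, without tests.
- Retitle Tables 14.2-4.1 to 14.2-4.3 so that the responder subset is not labelled ITT.

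The cost is SAP wording, three revised table shells, one added table and slightly more analysis work. Inferential statements within responders are lost. No new data are needed.
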